11.9. Analysis of immunogenicity

Analysis of binary variables:

The number and percentages of subjects will be summarized. Two-sided 95% CIs for the percentages will be computed.

Antibody titers/concentration below the limit of detection in the respective assay will be set to half the limit for the purposes of analysis. Missing values of immunogenicity will be excluded from analyses (i.e. complete-case analysis) since they are considered missing completely at random, i.e. not informative and with no impact on inferences.

Analysis of continuous variables:

The antibody concentrations/titers will be logarithmically transformed (base10) (to fulfil the normal distribution assumption). GMCs will be calculated, with their associated two-sided 95% CIs, by exponentiating the corresponding log-transformed means and their 95% CI.

Additionally, within-subject geometric mean ratios (GMRs) will be computed for geometric mean titers/GMCs at each time point after vaccination versus baseline (Day 1). The GMRs and 95% CIs will be constructed by exponentiating the mean within-subject differences in log-transformed titers and the corresponding 95% CIs.

205626 (S SONNEI MONO GMMA SBVGH-003 [H03_03TP])
Protocol Amendment 6 Final

11.10. Analysis of safety

The primary analysis will be performed on the All Exposed Set.

Analysis of solicited local and systemic adverse events and other reactions:

Solicited AEs will be summarized according to defined severity grading scales.

Frequencies and percentages of subjects experiencing each AE will be presented for each symptom severity. Summary tables showing the occurrence of any local or systemic AE overall and at each timepoint will also be presented.

Post-vaccination/challenge solicited AE reported from Day 1 to 7 days post-vaccination/challenge will be summarized by maximal severity and by vaccine/placebo group. The severity of solicited local AE will be summarized according to categories based on linear measurement.

Injection-site pain and systemic reactions occurring up to 7 days after each vaccination will be summarized according to "mild", "moderate" or "severe".

Each solicited local and systemic AE will also be further summarized as "none" versus "any".

Analysis of unsolicited AEs:

All the AEs occurring during the study, judged either as probably related, possibly related, or not related to vaccination/challenge by the investigator, will be recorded.

The original verbatim terms used by investigators to identify AEs in the eCRFs will be mapped to preferred terms using the MedDRA dictionary. The AEs will then be grouped by MedDRA preferred terms into frequency tables according to system organ class. All reported AEs, as well as AEs judged by the investigator as at least possibly related to study vaccine/placebo or challenge agent, will be summarized according to system organ class and preferred term within system organ class. These summaries will be presented by vaccination group. When an AE occurs more than once for a subject, the maximal severity and strongest relationship to the vaccine/placebo group will be counted.

Separate summaries will be produced for the following categories:

- SAEs.
- AEs that are possibly or probably related to vaccine/placebo or challenge agent.
- AEs leading to withdrawal from the study.

Data listings of all AEs will be provided by subject. In addition, AEs in the categories above will be provided as listed data.

205626 (S SONNEI MONO GMMA SBVGH-003 [H03_03TP])
Protocol Amendment 6 Final

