1.3.1. Risk assessment

Important Potential/Identified Risk	Data/Rationale for Risk	Mitigation Strategy
	Investigational vaccine: 1790GAHB va	accine
Symptomatic Neutropenia	Eight cases of Grade 2 or Grade 3 neutropenia were reported from Phase 1 clinical trials (asymptomatic). All cases occurred in the first 20	Exclusion criteria for this clinical study include: • Subjects with a low baseline neutrophil count below 1800 cells/µL (LLN).
	days after administration of first vaccine dose, and reversed after discontinuation.	 Previous history of Benign Ethnic Neutropenia, or drug related Neutropenia. Concomitant treatment with
	Literature review of reports of neutropenia in association with vaccination indicates factors noted to be associated with neutropenia (including ethnicity, and low baseline counts) with the majority of cases detected within 2 weeks of the vaccination. None of the reported cases was clinically symptomatic.	neutropenic agents. Monitoring for this clinical study to include: Baseline neutrophil counts. Full blood counts with differential measured at 7 days post each scheduled vaccination. Assessment of clinical impact of neutropenia. Subjects will be closely monitored
	Five cases of asymptomatic neutropenia (Grade 1 and 2) have been reported at Day 7 after receipt of the first dose in 5 subjects.	during the entire study and have hematology repeated every 7 days when neutropenia is identified until resolution. If a case of neutropenia does not resolve based on most recent available laboratory results, before the
	One of the 5 subjects had an additional Grade1 neutropenia episode at Day 28, and another one had two additional episodes, one of which was Grade 3 (940 cells/mL) at 7 days after the second dose and the second was Grade 2 (1,410 cells/mL) at 28 days after second vaccination. All cases were resolved before last study visit.	second vaccination, or challenge agent administration, the subject will not be revaccinated or administered the challenge agent.

205626 (S SONNEI MONO GMMA SBVGH-003 [H03_03TP]) Protocol Amendment 6 Final

	Protocol Amendment 6 Fin								
Important Potential/Identified Risk	Data/Rationale for Risk	Mitigation Strategy							
	Study Procedures								

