11.4. Determination of sample size

Primary objective - Efficacy

In comparing the protective efficacy of 1790GAHB vaccine against the placebo group the following assumptions will be made:

Assuming a true VE of 70%, a total number of 21 confirmed cases will be needed to demonstrate that the LL of the two-sided 90% CI for the VE is above 0% with 80% power (by Pass 2013, One Proportion Power Analysis, one-sided test, one-sided alpha = 5%).

Based on the results obtained by the Cincinnati Children's Hospital Medical Center, where the challenge model was developed, in subjects receiving a challenge with 1500 CFU of *S. sonnei* 53G, the attack rate for the primary case definition of this study is 58%. Thus considering an AR of 58% in the placebo group and a percentage of non-evaluable subjects of 22%, approximately 72 subjects (36 per group) will be recruited to reach these 21 cases.

The assumption on the value of true VE is based on the percentage of subjects with seroresponse observed in previous studies where the 1.5/25 µg OAg/protein dose of 1790GAHB vaccine was evaluated. In the phase I study in Europe, the observed percentage of subjects with seroresponse was 63% and 88% after 1st and 2nd vaccination respectively. In the Phase IIa study, conducted in endemic region, the observed percentage of subjects with seroresponse was 68% and 90% after 1st and 2nd vaccination, respectively.

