11.5.2. All Exposed Set

All subjects in the enrolled set who receive a study vaccination.

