11.5.3. Safety set

11.5.3.1. Solicited Safety Set (solicited local and systemic adverse events and other solicited adverse events)

All subjects in the Exposed Set with any solicited AE data and/or indicators of solicited AEs.

205626 (S SONNEI MONO GMMA SBVGH-003 [H03_03TP])
Protocol Amendment 6 Final

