11.5.3.2. Unsolicited Safety Set (unsolicited adverse events)

All subjects in the Exposed Set with unsolicited AE data.

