11.5.6. Other analysis sets

There are no additional analysis sets for analysis in this study.

All subjects who are screened, i.e., consented but not yet randomized/enrolled.

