11.6. Derived and transformed data

- Screening (anti S. sonnei LPS IgG Screening-ELISA)
 - The cut-off value for the anti *S. sonnei* LPS IgG Screening-ELISA is defined by the laboratory.
 - A seronegative subject is a subject whose titer is below the cut-off value.
 - A seropositive subject is a subject whose titer is greater than or equal to the cutoff value.
- Immunogenicity (anti *S. sonnei* LPS IgG-ELISA):
 - The cut-off value for the anti *S. sonnei LPS* IgG-ELISA is defined by the laboratory.

Seroresponse is aimed to define a significant increase in anti *S. sonnei* LPS IgG concentration in post-vaccination samples and relies on the definition already used in a previous phase II study in Kenyan population. For the purpose of this study seroresponse is defined as:

- If the baseline value is greater than 50 EU/mL then an increase of at least 50% in the post-vaccination sample as compared to baseline.
- If the baseline value is less or equal to 50 EU/mL then an increase of at least
 25 EU/mL in the post-vaccination sample as compared to baseline.

Note: Threshold values/increases given in the definition of seroresponse might be subject to change during the course of the study (e.g., in case of optimization/qualification/validation of the anti *S. sonnei* LPS IgG ELISA).

- The GMC calculations are performed by taking the anti-log of the mean of the log concentration transformations. Values to be used for the antibody concentrations below the assay cut-off will be described in the Statistical Analysis Plan (SAP).
- Handling of missing data: for a given subject and a given immunogenicity measurement, missing or non-evaluable measurements will not be replaced.

205626 (S SONNEI MONO GMMA SBVGH-003 [H03_03TP])
Protocol Amendment 6 Final

- Reactogenicity and safety:
 - Handling of missing data: subjects who missed reporting symptoms
 (solicited/unsolicited or concomitant medications) will be treated as subjects
 without symptoms (solicited/unsolicited or concomitant medications,
 respectively). In case of significant non-compliance of study procedures for
 reporting symptoms, the analysis plan will be reassessed to ensure more accurate
 reporting of study data by further analysis.
 - For the analysis of solicited symptom, missing or non-evaluable measurements will not be replaced. Therefore, the analysis of the solicited symptoms based on the All Enrolled Set will include only subjects/doses with documented safety data (i.e., symptom screen completed).

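### Post-challenge safety is summarised on everyone vaccinated, with no set of challenged subjects, so unsolicited AE, SAE and AESI rates after challenge can be diluted and the solicited AE denominator is contradictory

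*Protocol*

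**What the plan says.** Safety after challenge is a secondary objective of its own (Protocol 2.2, Safety), covering SAEs, unsolicited AEs, AESIs and laboratory parameters. Section 11.2 has unsolicited AEs within 28 days after challenge as an endpoint.

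Section 11.10 opens with "The primary analysis will be performed on the All Exposed Set" and then describes solicited summaries after vaccination or challenge, and unsolicited AEs related to vaccine, placebo or challenge agent. The populations in section 11.5 are:

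- All Exposed Set (11.5.2): "All subjects in the enrolled set who receive a study vaccination".
- Solicited Safety Set (11.5.3.1): "All subjects in the Exposed Set with any solicited AE data and/or indicators of solicited AEs".
- Unsolicited Safety Set (11.5.3.2): "All subjects in the Exposed Set with unsolicited AE data".
- Overall safety set (11.5.3.3): anyone in either of the last two.
- Other sets (11.5.6): "There are no additional analysis sets for analysis in this study".

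None of these requires the challenge agent to have been given.

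The protocol foresees vaccinated subjects who are not challenged. Section 3.2 bars challenge for fever, acute illness, or a course of antibiotics in the preceding week. Sections 7.5 and 9.2.1 bar it for pregnancy. For neutropenia that has not resolved, section 1.3.1 says that "the subject will not be revaccinated or administered the challenge agent". Under section 10.2.2 a subject withdrawn from the challenge agent need not leave the study.

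**The concern.** The trial has two exposures, the vaccine and the challenge strain, but only the first defines who counts as exposed. A subject who is vaccinated, barred from challenge and kept in follow-up belongs to every safety set, yet has no post-challenge period. In a table of events after challenge, that subject adds to the denominator and cannot add to the numerator. The percentage then describes vaccinated subjects, whereas the objective in section 2.2 concerns what happens after challenge.

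Two things are at stake. The first is the level of the post-challenge rates in each arm. The second is the comparison between arms, if the share unchallenged differs. Symptomatic neutropenia is the only risk listed for the investigational vaccine in section 1.3.1, and unresolved neutropenia is a bar to challenge, so a difference by arm is conceivable.

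**Working it through.** **1. Is there a plan figure to reproduce?** The protocol states no post-challenge AE rate and no expected number unchallenged. The nearest figure is in section 11.4: "a percentage of non-evaluable subjects of 22"%. It belongs to the efficacy sample size, which reproduces:

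- Cases needed: 21. Placebo attack rate: 0.58. VE: 70%, so the two arms together yield 0.58 × (1 + 0.30) = 0.58 × 1.3 cases per pair of subjects.
- Evaluable per arm: 21 / (0.58 × 1.3) = 27.9.
- Enrolled per arm: 27.9 / 0.78 = 35.7, so 36 per arm and 72 in total.

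The 22% is therefore an allowance for subjects not evaluable for efficacy. Nothing says how many of them would be unchallenged.

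**2. Dilution of a post-challenge rate.** Let r be the event rate among challenged subjects and d the share of an arm that was vaccinated but not challenged. If those subjects stay in the denominator and contribute no post-challenge event,

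reported rate = r × (1 - d).

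| Assumed d | Approximate subjects of 36 | Multiplier on each rate |
|---|---|---|
| 0% | 0 | 1.00 |
| 5% | 36 × 0.05 = 1.8 | 0.95 |
| 10% | 36 × 0.10 = 3.6 | 0.90 |

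**3. Effect on the comparison.** With shares d_v (vaccine) and d_p (placebo),

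reported ratio = true ratio × (1 - d_v) / (1 - d_p).

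If d_v = d_p the factor is 1 and the ratio is undistorted. If, purely for illustration, d_v = 10% and d_p = 5%, the factor is 0.90 / 0.95 = 0.947. The protocol gives no per-arm figure from which to choose these values.

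**4. Which tables does this reach?** The two relevant rules of section 11.6 side by side:

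| | First rule | Second rule |
|---|---|---|
| Scope | Subjects who missed reporting: "solicited/unsolicited or concomitant medications) will be treated as subjects" without symptoms | Solicited symptoms only |
| Handling | Counted as symptom-free | Not replaced; only subjects or doses with documented safety data are analysed |
| Set named | None | All Enrolled Set |

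- *Unsolicited AEs, SAEs, AESIs.* The documented-data restriction does not cover them. The set in section 11.10 supplies the denominator, and step 2 applies.
- *Solicited AEs after challenge.* Under the second rule an unchallenged subject, who has no post-challenge record, drops out and there is no dilution. Under the first rule, if it is read to include that subject, there is. The text does not settle which applies.
- *Set name.* The second rule refers to the All Enrolled Set, which under section 11.5.1 takes in screened subjects whatever their randomisation or treatment status. Section 11.10 names the All Exposed Set. These are different populations.

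**The case against.** The strongest reply is that section 11.10 names a set for the primary safety analysis without fixing a denominator for each table, and that period-specific denominators are commonly left to the SAP. That is fair in general. Here, however, the protocol names the population, builds all its safety sets on vaccination and states that there are no others. A SAP using challenged subjects would have to depart from section 11.5.6.

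It can also be said that AEs are listed by subject, so rates per challenged subject could be recovered, and that section 11.11 makes comparisons without a success criterion descriptive. Both points stand and limit the consequence. They do not make the tabulated percentage the right one for the objective.

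A reader might go further and infer any of the following, none of which the protocol supports:

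- *That every unchallenged subject must count as symptom-free in every post-challenge table.* The documented-data rule would remove such subjects from solicited tables, and a person never challenged has not obviously missed reporting.
- *That 22% of subjects will be unchallenged.* That figure is an efficacy allowance and may include challenged subjects excluded from the per-protocol set.
- *That the 58% attack rate can stand in for a safety event rate.* It is the rate for the primary shigellosis definition, which is analysed on sets requiring efficacy data.
- *That the vaccine arm will be diluted more, so the vaccine will seem to reduce post-challenge AEs.* Only unresolved neutropenia bars challenge, section 7.5 allows re-evaluation beforehand, and the earlier cases described in section 1.3.1 reversed or resolved.

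**Conclusion.** The point holds in a limited form. The protocol fixes a vaccination-based population for post-challenge safety and closes the list of sets, so rates of unsolicited AEs, SAEs and AESIs after challenge can be understated by the factor (1 - d). At assumed shares of 5% and 10% unchallenged, the factors are 0.95 and 0.90. This rests on two assumptions: that some vaccinated subjects are not challenged and remain in the set, which the protocol permits, and that they contribute no post-challenge events. The size of d is unknown from the document.

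Distortion between arms requires d to differ by arm. That is possible through neutropenia but is not shown. For solicited post-challenge AEs, the finding is a contradiction in section 11.6 and not an established dilution. The primary efficacy test is unaffected. This is a correction to descriptive safety reporting, worth making because the right denominator is easily defined.

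**What to change.** - In section 11.5, define a Challenged Safety Set: all subjects who received the challenge agent, grouped by the vaccine or placebo actually received.
- In section 11.10, use it as the denominator for all post-challenge safety summaries: solicited and unsolicited AEs, SAEs, AESIs and laboratory parameters. Keep the All Exposed Set for post-vaccination safety.
- Amend section 11.5.6 so that it no longer excludes such a set.
- In section 11.6, reconcile the two missing-data rules, stating which applies to solicited and which to unsolicited events, and that a subject never challenged is not a non-reporter for the post-challenge period. Replace the All Enrolled Set with the set that section 11.10 uses.
- Report by arm the number vaccinated but not challenged, with reasons, so that any imbalance is visible.

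The cost is protocol and SAP wording and one population flag. No new data are needed, and the sample size and efficacy analysis do not change.

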11.11. Interpretation of analyses

Except for analyses on objectives with a predefined success criterion and an appropriate type I error control (see Section 2), comparative analyses will be descriptive with the aim to characterize the difference in reactogenicity and immunogenicity efficacy between groups. These descriptive analyses should not be interpreted.

11.12. Conduct of analyses

Any deviation(s) or change(s) from the original statistical plan outlined in this protocol will be described and justified in the final study report.

11.12.1. Sequence of analyses

The total of 72 subjects will be divided in 4 cohorts of 18 subjects each (for bed availability at the study site). The vaccination and challenge will be done per cohort. However, if for any reason, a cohort does not reach the planned 18 subjects, additional subjects can be added in the next cohorts. The maximum number of subjects must not be more than 20 (maximum number of beds in the clinic) in each cohort.

The following 2 interim analyses are planned:

- 1. After completion of the Visit 5 (Day 64): post-challenge efficacy data of all subjects (all 4 cohorts)
- 2. After Visit 6 (Day 85): secondary immunogenicity data and tertiary SBA immunogenicity data of all subjects (all 4 cohorts).

(Amended: 23 July 2019)

All analyses will be conducted before unblinding on *clean and final* data. (Amended: 23 July 2019)

An integrated Clinical Study Report containing all data will be written after the End of Study and made available to the investigators. (Amended: 23 July 2019)

If the data for tertiary endpoints become available at a later stage, (an) additional analysis/analyses will be performed. These data will be documented in annex(es) to the study report and will be made available to the investigators at that time.

11.12.2. Statistical considerations for interim analyses

No statistical adjustment will be made for the interim analyses, which are intended to provide final outputs related to the different endpoints and timepoints in a phased manner.

205626 (S SONNEI MONO GMMA SBVGH-003 [H03_03TP])
Protocol Amendment 6 Final

12. ADMINISTRATIVE MATTERS

To comply with ICH GCP administrative obligations relating to data collection, monitoring, archiving data, audits, confidentiality, public disclosure requirements and publications must be fulfilled.

12.1. Electronic case report form instructions

A validated GSK defined electronic data collection tool will be used as the method for data collection.

In all cases, subject initials will not be collected nor transmitted to GSK. Subject data necessary for analysis and reporting will be entered/transmitted into a validated database or data system. Clinical data management will be performed in accordance with applicable GSK standards and data cleaning procedures.

While completed eCRFs are reviewed by a GSK Biologicals' Site Monitor at the study site, omissions or inconsistencies detected by subsequent eCRF review may necessitate clarification or correction by the investigator or appropriately qualified designee. In all cases, the investigator remains accountable for the study data.

The investigator will be provided with an electronic format in read only mode of the final version of the data generated at the investigational site once the database is archived and the study report is complete and approved by all parties.

12.2. Subject Diary

Paper Diaries (pDiaries), hereafter referred to as Subject Diaries will be the only source document allowed for solicited local and systemic adverse events (including body temperature measurements), starting after the initial 30 minute post-vaccination period at the clinic. The following additional rules apply to documentation of safety information collected in the Subject Diary.

The Investigator or delegated staff should monitor the Subject's Diary status throughout the study for compliance and any solicited local and systemic adverse events that were of concern to the subject.

- No corrections or additions to the information recorded by the subject within the Subject Diary will be allowed after it is delivered to the site.
- Any blank or illegible fields on the Subject Diary must be described as missing in the eCRF.

The following additional rules apply to documentation of Subject Diary information collected in the eCRFs:

• The site must enter all readable entries in the Subject Diary into the eCRF, including those values that may be biologically implausible (e.g. body temperature: 400°C).

205626 (S SONNEI MONO GMMA SBVGH-003 [H03_03TP])
Protocol Amendment 6 Final

- Any illegible or implausible data should be reviewed with the Subject. If an underlying solicited or unsolicited AE is described on review with the subject, this should be described in the source document and reported as an unsolicited AE in the Adverse Event eCRF (e.g., if the subject above confirms body temperature of 40°C on the day in which body temperature: 400°C was written into his/her Subject Diary, this fever of 40°C should be recorded in the Adverse Event eCRF).
- Any newly described safety information (including a solicited AE) must not be written into the Subject Diary and must be described in the study file as a verbally reported AE. Any AE reported in this fashion must be described as an unsolicited AE and therefore entered on the Adverse Event eCRF.

